8.2.1 Fertile women

In fertile women measurement of human chorionic gonadotropin must be negative prior to randomization. A woman is considered of childbearing potential (WOCBP), i.e. fertile, following menarche and until becoming post-menopausal unless permanently sterile. Permanent sterilization methods include hysterectomy, bilateral salpingectomy and bilateral oophorectomy. A postmenopausal state is defined as no menses for 12 months without an alternative medical cause.

8.2.2 Contraception

Highly effective contraception (failure rate $< 1\%$ pr. year) is defined as one of the following;

- combined (estrogen and progestogen containing) hormonal contraception associated with inhibition of ovulation
 - oral
 - intravaginal
 - transdermal
- progestogen-only hormonal contraception associated with inhibition of ovulation
 - oral

- injectable
- implantable
- intrauterine device (IUD)
- intrauterine hormone-releasing system (IUS)
- bilateral tubal occlusion
- vasectomised partner
- sexual abstinence

Contraception must continued until 3 days after the last visit.

9 Number of centers & patients:

9.1 Planned number of centers:

The following tertiary centers will participate:

Site A

Department of Cardiology,
Odense University Hospital
[name]
[name]

Site B

Department of Cardiology
Rigshospitalet
[name]
[name]

Sponsor and principal investigator at site A

[name] [name], MD PhD DmSc
Phone
E-mail

Principal investigator at site B

[name], PhD, DmSc
Phone:
E-mail:

9.2 Total number of patients:

In total one hundred patients are planned to be randomized according to sample size estimation, 50 patients in each arm.

10 Collaborators

Production of study medication, matching placebo, packing and handling of study medication:

Sygehusapotek Fyn, hovedapotek
[name],

[name]
Denmark

GCP-monitoring:

GCP-enheden
Odense Universitetshospital
[name]
[name]
Denmark

Data management and randomization:

Odense Patient data Explorative Network (OPEN)
[name]
[name]
Denmark

Storage and analysis of blood samples

Department of Clinical Biochemistry and Pharmacology
[name]
[name]
Denmark

11 Evaluation schedule:

| Visit number | 0 | 1 | 2 | 3 |
|--|--------------|-----------------|-----------------|----------------|
| Time of Visit | day 1 | week 2-4 | Week 4-6 | month 6 |
| Inclusion/Exclusion criteria | x | | | |
| Information & Informed consent | x | | | |
| Physical examination | x | x | x | x |
| Vital signs (pulse and blood pressure) | x | x | x | x |
| Spirometry | x | | | |
| Echocardiography | x | | | x |
| Right heart catheterization | x | | | x |
| Cardiac MRI | x | | | x |
| Dispense study medication | x | x | x | x |
| Laboratory test ^a | x | x | x | x |
| Concomitant medication | x | x | x | x |
| Adverse events | | x | x | x |

^a Unblinded measurements: Hemoglobin, platelet count, white blood cell count(WBC), WBC differential, alanine aminotransferase (ALT), albumin, total bilirubin, alkaline phosphatase, blood urea nitrogen, calcium, creatinine, potassium, sodium, glucose, lipid profile(total cholesterol, LDL, HDL and triglycerides). Additional blood samples are drawn and stored for later analysis of NT-proBNP, MR-pro-ANP, ST2 and possible future biomarkers.

Patients who meet the study inclusions and none of the exclusion criteria will after signing an Ethics Committee approved Informed Consent Form, will undergo conventional spirometry, blood testing, comprehensive resting Doppler echocardiography, cardiac MRI with late enhancement imaging, resting right heart catheterization, and symptom-limited supine cycle exercise test with simultaneous echocardiography and right heart catheterization will be performed before randomization.

After randomization patients will be started on LCZ696 49/51 mg twice daily or matching placebo twice daily titrated to their final doses of LCZ696 97/103 mg twice daily or matching placebo twice daily over a period of 2–4 weeks. Succeeding up titration to final dose a visit is planned after two weeks (visit 2) to assess tolerability. In case of clinical concern regarding tolerability additional follow up is left at discretion of the investigator.

Background therapy will be decided at the discretion of treating physicians. The double-blind design will continued for 26 weeks. After 26 weeks treatment cardiac MRI, echocardiography, right heart catheterization and exercise test will be repeated.

Patients will in addition to the above mentioned be followed in the “Prevention and aftercare out-patient clinic” as per standard care following AMI.

11.1 Discontinuation of study treatment

Patients can voluntarily and for any reason discontinue study treatment and withdraw consent to participate at any time. If one of the following circumstances emerges study treatment will be discontinued

- Withdrawal of informed consent
- The investigator believes the study treatment has an overall negative influence on the patient’s wellbeing.
- Clinical suspicion of significant angioedema.
- Decline in kidney function assessed by an estimated glomerular filtration rate (eGFR) below 30 ml per minute per 1.73 m² of body-surface area.
- Symptomatic hypotension that is not overcome by appropriate actions as described in section 11.1.1

11.1.1 Hypotension

If symptomatic hypotension occurs treatable causes must be corrected, i.e. hypovolemia. Hypotension in euvolemic patients require through evaluation of concomitant medication. If possible concomitant medication may be reduced in dose or discontinued. If hypotension persists in patients receiving 97/103 mg or matching placebo treatment dose can be reduced to 49/51 mg or matching placebo.

11.2 Hemodynamic stress echocardiography:

Transthoracic echocardiography, including additional images for regional tissue Doppler and 2D speckle tracking analysis and 3D analysis, will be performed at rest. All of these images will be recorded by an experienced echocardiographer on GE Vivid 9 ultrasound machine and stored digitally. Guided by ultrasound a 7Fr-Swan-Ganz catheter is placed via the right internal jugular vein. The catheter is advanced into wedge position. Simultaneous with echocardiography resting pulmonary arterial pressure, mean right atrial pressure, cardiac output and wedge pressure is measured. Cardiac output is estimated by thermodilution as a mean of 3 measurements with less than 10% variation. At each exercise level a central venous blood sample will be taken for measurement of central venous oxygen saturation, pH and lactate. Arterial blood pressure is measured noninvasively and is repeated every third minute during the stress test. ECG and arterial saturation is measured continuously. The resistance is increased with 25W every third minute until exhausting.

The following echocardiographic images will be saved at each exercise level and after 5 minutes of rest: Apical 2, 4 chamber images with zoom on the LV cavity zoom of RV cavity; PW Doppler mitral inflow; PW Doppler LVOT flow.

At every exercise level the following parameters are measured: Pulmonary arterial systolic, diastolic and mean blood pressure; Central venous pressure; Arterial saturation; Heart rate; Cardiac output and PCWP.

11.3 Blood samples

Before invasive stress test and at every visit venous blood samples will be taken and stored as frozen plasma for analyzes of plasma ST2 using an enzyme-linked immunosorbent assay NT-proBNP, plasma MR-pro-ANP, and possible other further analyses. In addition eGFR will be assessed at each visit.

11.4 Cardiac magnetic resonance imaging

Patients will be screened for contraindications for MRI, and if none exist MRI-scan will be performed before randomization and repeated after 26 weeks using a 1.5T scanner (Siemens Healthcare Solutions, Forchheim, Germany) with a 32-channel cardiovascular array coil (InVivo, Orlando, Florida, USA). Images will be obtained 10 minutes after intravenous injection of 0.1-mmol/kg body weight gadolinium-diethylenetriamine pentaacetic acid (Gadovist, Bayer Schering, Berlin, Germany). An 11-heart-beat modified Look Locker sequence with inversion recovery will be used for T1 mapping. Slice thickness 8 mm, slice gap 0 mm, echo time 1.4 ms, resolution matrix 192 x 192, field of view 300–360 mm. In a single slice the inversion time was adjusted to null the signal from the normal myocardium, after which time multiple slices in the short-axis image plan will be acquired covering the entire LV. The endocardial and epicardial borders will be manually traced in all short axis images and the LV mass was calculated. Papillary muscles will be considered as part of the LV cavity.

Late gadolinium enhancement will be assessed semiquantitatively, using the American Heart Association 17 segment model and giving each segment a score from 0 to 4 depending on the extent of scar (0: no scar, 4: 100% scar). A final score is given by the summation of all segments' scores and division of the result by number of segments. In addition diffuse fibrosis will be assessed using T2 weighted images.

11.5 Investigational & Reference Therapy:

| Treatment Arm | # of Patients Entered Treatment | Type of Study Drug | Compound | Min Dose | Max Dose | Frequency | Admin. Route | Generic Acceptable? (applies only for comparator) |
|---------------|---------------------------------|--------------------|----------|----------|----------|-----------|--------------|---|
| | 100 | Investigational | LCZ696 | | 400 | Daily | Oral | No |
| | | Comparator | Placebo | | | | Oral | |

12 Ethical considerations:

The study will not be initiated before relevant authorities including The regional committee of science ethics for the Region of Southern Denmark have approved the study. Informed consent will be obtained according to national and international legislation. Below is a detailed description of risks with the planned procedures and medication. As described earlier diastolic dysfunction following AMI is associated with increased mortality and morbidity. The optimal treatment for this large group of patients is incompletely understood. In this light, neither the individual procedures or the study as whole is indefensible.

12.1 Risk of procedures

Placement of the Swan-Ganz catheter is associated with a low risk of complications. A hematoma can develop around the location of the placement sheath, which usually doesn't require treatment. Rarely perforation of the right atrium or ventricle (less than 1:1000) has been reported. This is usually treated by extraction guided by ultrasound (pericardiocentesis), but operation can be required. Arrhythmias that require treatment (cardioversion) may rarely be seen. All participating sites have extensive experience in performing invasive exercise testing. At the participating centres more than 250 patients have been evaluated with the technique with no serious adverse events.

The most common side effects of MRI contrast agent (Gadoterinsyre (Dotarem®)) are brief transient headache, nausea and dizziness following the injection. This occurs in 1% to 5% of contrast injections. Allergic reactions to gadolinium contrast medium have occurred but are extremely rare (less than 1 in 10,000). As gadolinium contrast medium in patients with kidney failure (either chronic or acute) has been associated with nephrogenic systemic fibrosis, Gadoterinsyre despite being classified as a low-risk agent by EMA will not be used in patients with eGFR < 30 ml/min/1,73 m².

12.2 Risk of LCZ696

In previous clinical trials LCZ696 has been well tolerated (10,11). Because of its vasodilator effects, treatment with LCZ696 may be associated with symptomatic hypotension. In previous studies this has not been associated with increased risk of renal failure and has not been associated with increased discontinuation rate (10,11). Previous studies have not indicated increased risk of hyperkalemia or angioedema with LCZ696 (10,11).

13 Pharmacovigilance requirements:

Any SUSAR will immediately be reported to Danish Medicines Agency and the Regional Ethics Committee of Southern Denmark. Fatal SUSAR's or life threatening reactions will be reported within 7 days after sponsor has knowledge of the event. Sponsor will provide detailed follow-up information regarding the event within 8 days. Other SUSAR's will be reported within 15 days of knowledge. The product resume for LCZ696 is reference document when assessing adverse events.

13.1 Adverse events (AE)

Information about all AEs, whether volunteered by the patient, discovered by investigator questioning, or detected through physical examination, laboratory test or other means, will be collected and recorded on an Adverse Event Case Report Form and will be followed up as appropriate.

An AE is any undesirable sign, symptom or medical condition occurring after starting study treatment, even if the event is not considered to be treatment-related. Study treatment includes the study medication under evaluation, and any reference or placebo drug (or therapy) given during any phase of the trial.

Medical conditions/diseases present before starting study treatment will only be considered adverse events if they worsen after starting study treatment (any procedures specified in the protocol). Adverse events (but not serious adverse events) occurring before starting study treatment but after signing the informed consent form will be recorded on the Medical History/Current Medical Conditions Case Report Form. Abnormal laboratory values or test results constitute adverse events only if they induce

clinical signs or symptoms, are considered clinically significant or require therapy, and are recorded on the Adverse Events Case Report Form under the signs, symptoms or diagnosis associated with them.

As far as possible, each adverse event will also be described by:

1. the severity grade (mild, moderate, severe)
2. its relationship to the drug of interest (suspected/not suspected)
3. its duration (start and end dates or if continuing at final exam)
4. whether it constitutes a serious adverse event (SAE)

13.2 Serious Adverse Events (SAEs)

Information about all serious adverse events will be collected and recorded on the Serious Adverse Event Report Form.

An SAE is defined as an event which:

- Is fatal or life-threatening
- Results in persistent or significant disability/incapacity
- Constitutes a congenital anomaly/birth defect
- Requires inpatient hospitalization or prolongation of existing hospitalization, unless hospitalization is for:
 - Routine treatment or monitoring of the studied indication, not associated with any deterioration in condition (specify what this includes)
 - Elective or pre-planned treatment for a pre-existing condition that is unrelated to the indication under study and has not worsened since the start of the drug of interest
 - Social reasons and respite care in the absence of any deterioration in the patient's general condition
- Is medically significant, i.e., defined as an event that jeopardizes the patient or may require medical or surgical intervention to prevent one of the outcomes listed above e.g. may require treatment on an emergency outpatient basis for an event not fulfilling any of the definitions of a SAE given above and not resulting in hospital admission
- Transmission of infectious agent via medicinal product

Any SAEs exempt from this reporting process must be clearly identified in the study protocol with a scientific/medical justification e.g. SAEs due to disease progression, SAEs due to a planned surgical procedure, etc.

Any SAE occurring after the patient has provided informed consent and until 4 weeks after the patient has stopped study participation will be reported.

As far as possible, each SAE will also be described by (but not limited to):

- Its duration (onset date = date of 1st signs or symptoms, and end dates)
- The seriousness criteria and severity if applicable (mild, moderate, severe)
- Its relationship to current investigational drug (suspected / not suspected as judged by the investigator),

- The action(s) taken and investigation results if applicable
- Concomitant medication details
- Outcome

13.3 SUSAR

Any SUSAR will immediately be reported to Danish Medicines Agency and the Regional Ethics Committee of Southern Denmark. Fatal SUSAR's or life threatening reactions will be reported within 7 days after sponsor has knowledge of the event. Sponsor will provide detailed follow-up information regarding the event within 8 days. Other SUSAR's will be reported within 15 days of knowledge.

14 Data collection

Data is collected from hospital records and results from echocardiography, exercise testing and cardiac MRI. Data from the exercise testing is written directly in the electronic case report form, all other data are copied from other sources. Information that is needed for the study before the patient have given consent is disclosed to the investigators.

14.1.1 Access to data

In the written information to patients, it is specified that when given consent to participate in the study patients also allow that investigators, the GCP-unit and control authority (Danish Medical Agency) have access to all data collected in the study and hospital records (including electronic records). Access are allowed in order to conduct mandatory monitoring and control.

15 Data analysis

Data required by the protocol will be entered into an internet based Electronic Case Report Form using fully validated RedCap software. Data storage will be managed by Odense Patient data Explorative Network (OPEN). The full analysis set will consist of all randomized patients. Following the intent to treat principle, patients will be analyzed according to the treatment to which they were assigned at randomization, and efficacy variables will be analyzed based on the full analysis set.

15.1 Baseline characteristics

Summary statistics will be provided by treatment group for demographics and baseline characteristics. Continuous variables will be summarized using n, mean, standard deviation, median, 25'th and 75' percentile. Categorical variables will be summarized using frequency and percentage. The difference between treatment groups will be compared using the Chi-square test for categorical variables or using t-test for continuous variables. A p value <0.05 will be considered statistically significant.

15.2 Analysis of primary endpoint

Primary endpoint, PCWP/CI ratio, will be analyzed using ANCOVA with treatment as fixed effect factor. Additionally, the baseline value of the corresponding variable may be included as a covariate if appropriate. The estimated treatment effect and the corresponding two-sided 95% confidence interval will be provided.

15.3 Analysis of secondary endpoints

The secondary hypotheses will be tested and statistical inferences will be made only if the primary hypothesis is rejected. The five secondary efficacy variables will be tested for superiority of LCZ696 to placebo for all randomized patients following the intent-to-treat principle.

16 Funding

The study is conducted independently of the manufacture and is thus supported by Hjerteforeningen, OUH-RH puljen and OUH's frie forskningsmidler. None of the investigators has financial attachment to the manufacture.

17 Presentation of data and timeframe

All results from the study will be published in international peer reviewed scientific journals irrespective of a positive, negative or neutral result. It is anticipated that the main hypothesis will generate a publication in a top ranking cardiologic journal. The study is expected to start June 2018 and be finalized May 2021 with presentation of main results November 2021 at the American Heart Association Scientific Sessions.

18 Key-references

3. Hillis GS, [name] JE, Pellikka Pa, et al. Noninvasive estimation of left ventricular filling pressure by E/e' is a powerful predictor of survival after acute myocardial infarction. *Journal of the American College of Cardiology*. 2004;43:360-367.
4. [name] JE, Whalley Ga, Dini FL, et al. Independent prognostic importance of a restrictive left ventricular filling pattern after myocardial infarction: an individual patient meta-analysis: Meta-Analysis Research Group in Echocardiography acute myocardial infarction. *Circulation*. 2008;117:2591-2598.

Statistical analysis plan for

ANGIOTENSIN-NEPRILYSIN INHIBITION IN DIASTOLIC DYSFUNCTION

AFTER AMI

the ARNiAMI study

1 Data analysis

Data required by the protocol will be entered into an internet based Electronic Case Report Form using fully validated RedCap software. Data storage will be managed by Odense Patient data Explorative Network (OPEN). The full analysis set will consist of all randomized patients. Following the intent to treat principle, patients will be analyzed according to the treatment to which they were assigned at randomization, and efficacy variables will be analyzed based on the full analysis set.

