The main objective of this study is to assess the effect of angiotensin–neprilysin inhibition on central hemodynamics, myocardial structure and myocardial function in patients with a recent AMI and Doppler echocardiographic signs of diastolic dysfunction and preserved systolic function.

5.1 Primary objective:

To assess the effect of 6 months treatment with LCZ696 compared with placebo on ratio of PCWP/CI during exercise in patients with a recent AMI and Doppler echocardiographic signs of diastolic dysfunction and preserved systolic function.

5.2 Secondary objectives:

To assess the effect of 6 months treatment with LCZ696 compared with placebo in patients with a recent AMI and Doppler echocardiographic signs of diastolic dysfunction and preserved systolic function on:

1. Cardiac fibrosis assessed on cardiac magnetic resonance imaging,
2. The ST2 cardiac biomarker
3. Left atrial size and function
4. MR-proANP and NT-proBNP
5. Diastolic dysfunction assessed by Doppler echocardiography

5.3 Primary endpoint:

Ratio of pulmonary capillary wedge pressure to cardiac index at peak exercise after 26 weeks treatment with LCZ696 or placebo.

5.4 Secondary endpoints:

1. Amount of hyperenhancement on cardiac MRI using a semiquantitative assessment of late gadolinium hyperenhancement in a 17 segment model of the LV.
2. ST2 concentration at rest.
3. Left atrial volume by echocardiography and left atrial emptying fraction by echocardiography at rest.
4. MR-proANP and NT-proBNP concentration at rest.
5. Proportion of patients with moderate or severe diastolic dysfunction at rest.

6 Methodology:

The ARNiAMI study is a prospective, multicenter, randomized, double blind clinical trial to evaluate the efficacy, of LCZ696 97/103 mg BID versus matching placebo in subjects aged 50 years or older with a recent documented AMI, diastolic dysfunction and LVEF $\geq 45\%$ on cardiac physiology and myocardial fibrosis. Patients who meet the study inclusions and none of the exclusion criteria will after signing an Ethics Committee approved Informed Consent Form, be asked to undergo baseline procedures for the study.

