6.1.3 Sample size

Based on previous data it is expected that PCWP will increase to 32 ± 8 mmHg and cardiac index to 7.4 ± 1.4 l/min/m², with a PCWP/CI ratio of 4.49 ± 1.4 (19).

To detect a decrease of 20% in primary endpoint with alpha of 0.05 and beta 0.8, a total of 90 patients are required, to allow 10% dropout rate 100 patients are expected to be enrolled.

| Difference in PCWP/CI ratio | Standardized difference | N (Total) $\alpha=0.05/\beta=0.8$ | N (Total) $\alpha=0.05/\beta=0.9$ |
|-----------------------------|-------------------------|--------------------------------------|--------------------------------------|
| 10% (0.449) | 0.299 | 320 | 450 |
| 15% (0.674) | 0.449 | 150 | 200 |
| 20% (0.898) | 0.598 | 90 | 110 |
| 25% (1.12) | 0.748 | 70 | 100 |

7 Timelines and Study duration:

Start date: June 2018

Approval from relevant authorities: Medio august 2018

Inclusion start: 1/9 2018

Last patient last visit: July 2020

End date: July 2020

Clinical study report date: August 2020

Publication date: September 2020 – May 2021

8 Population:

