1.2 Analysis of primary endpoint

Primary endpoint, PCWP/CI ratio, will be analyzed using ANCOVA or mixed effects models with treatment as fixed effect factor with the intention-to-treat principle. Additionally, the baseline value of the corresponding variable may be included as a covariate if appropriate. The estimated treatment effect and the corresponding two-sided 95% confidence interval will be provided.

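### The all-randomised efficacy analysis is promised but not secured: model and baseline adjustment are left open, missing week-26 values have no stated handling, and testing after stopping study drug is not addressed

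*SAP*

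**What the plan says.** - **Analysis set.** SAP section 1: "The full analysis set will consist of all randomized patients", and "efficacy variables will be analyzed based on the full analysis set". Protocol section 15 says the same.
- **Endpoint.** Protocol 5.3: "Ratio of pulmonary capillary wedge pressure to cardiac index at peak exercise after 26 weeks treatment with LCZ696 or placebo". The schedule in Protocol section 11 has right heart catheterisation at visit 0 and month 6 only. The first test precedes randomisation, so each patient has a planned baseline value and one planned later value.
- **Model.** Protocol 15.2: "Primary endpoint, PCWP/CI ratio, will be analyzed using ANCOVA with treatment as fixed effect factor". SAP 1.2: the endpoint "will be analyzed using ANCOVA or mixed effects models with treatment as fixed effect factor with the intention-to-treat principle". Both make baseline adjustment optional; in the SAP, "the baseline value of the corresponding variable may be included as a covariate if appropriate".
- **Expected loss.** Protocol 6.1.3: "to allow 10% dropout rate 100 patients are expected to be enrolled".
- **Stopping.** Protocol 11.1: "Patients can voluntarily and for any reason discontinue study treatment and withdraw consent to participate at any time". It then lists circumstances in which treatment stops, among them angioedema, eGFR below 30 and persistent symptomatic hypotension. It does not say what happens to later assessments.

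Neither document contains an imputation rule, a missing-data assumption or a sensitivity analysis.

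**The concern.** An ANCOVA of the week-26 value uses only patients who have that value. If 10% do not, the analysis set is in practice the patients who were tested at week 26, whatever it is called. Enrolling 100 to end with 90 protects power. It does nothing about bias if the patients lost differ between arms.

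Unequal loss is a plausible risk here. Protocol 12.2 says LCZ696 may cause symptomatic hypotension, and Protocol 11.1 makes persistent symptomatic hypotension a reason to stop. Protocol section 11 ties the repeat catheterisation to 26 weeks of treatment and does not mention patients who have stopped.

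Because the model is left open and baseline is optional, the analyst may choose an unadjusted comparison of completers and still call it intention to treat. The reader would then have no stated assumption to judge it by and no sensitivity analysis to show how far it can be trusted.

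**Working it through.** **1. The plan's own figure.** Inputs from Protocol 6.1.3: difference 0.898, standardised difference 0.598 (so SD = 0.898/0.598 ≈ 1.5), two-sided alpha 0.05, power 0.80 (printed as beta).

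n per arm = 2 × (1.96 + 0.842)² / 0.598² ≈ 43.9, so 44 per arm and 88 in total. The t-based version gives 45 per arm, 90 in total. Then 90/0.90 = 100, and the stated figures reproduce. At SD 1.5, power is 84% with 100 evaluable patients, 80% with 90 and 75% with 80. The planned loss is already paid for in precision; the open question is bias.

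**2. Bias by arithmetic.** If a share m of an arm is missing and those patients would have had values s higher than completers, the completer mean is too low by m × s. With the same s in both arms:

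bias = −(m_LCZ696 − m_placebo) × s

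Neither m by arm nor s is in the documents; both are assumed. Take the plan's 10 losses in 100, SD 1.5, and s of 0.5 to 1 SD (0.75 to 1.5):

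| Losses, LCZ696 v placebo | Difference in share | Bias | Share of 0.898 |
|---|---|---|---|
| 5 v 5 | 0 | 0 | 0% |
| 8 v 2 | 0.16 − 0.04 = 0.12 | −0.09 to −0.18 | 10% to 20% |
| 10 v 0 (extreme) | 0.20 | −0.15 to −0.30 | 17% to 33% |

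Negative values favour LCZ696. If s is negative, the sign reverses.

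**3. Loss that depends on baseline.** Simulation with no true effect, 50 per arm, loss in the LCZ696 arm only and more likely at high baseline PCWP/CI, baseline to week-26 correlation 0.5 (assumed):
- unadjusted completers: −0.093 at 11% loss and −0.148 at 19%; a separate run of the same scenario gave about −0.08 to −0.12;
- with baseline in the model: 0.005 and 0.002, that is, about zero.

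The range 0.08 to 0.15 is 0.08/0.898 = 9% to 0.15/0.898 = 17% of the target. The standard error is about 1.5 × √(1/45 + 1/50) = 0.31 at 11% loss and 1.5 × √(1/41 + 1/50) = 0.32 at 19%. The shift is therefore roughly 0.3 to 0.5 standard errors, which raises a two-sided 5% error rate to about 6–8%.

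**4. Loss that depends on the unseen outcome.** Simulation with 8/50 v 2/50 missing, no true effect, SD 1.5:

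| Correlation (assumed) | Unadjusted | Baseline-adjusted |
|---|---|---|
| 0.3 | −0.235 | −0.216 |
| 0.5 | −0.228 | −0.173 |
| 0.7 | −0.231 | −0.120 |

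Adjustment should leave a fraction of about 1 − r². At r = 0.5, 0.228 × 0.75 = 0.171, which agrees with 0.173. The remaining bias is 0.120/0.898 = 13% to 0.216/0.898 = 24% of the target.

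**5. Does the mixed model change this?** With baseline complete and one later value, the likelihood splits into a baseline part and a part for week 26 given baseline. Patients with baseline only inform the first part, not the treatment effect. A constrained-baseline model therefore gives the baseline-adjusted ANCOVA estimate. A version without the baseline constraint differed from it by at most 0.003 in every scenario simulated.

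**The case against.** A reader might infer that the intention-to-treat analysis cannot be delivered. The documents do not support that. SAP 1.2 offers mixed effects models, and since the baseline test precedes randomisation, a two-visit mixed model can include every randomised patient with a baseline value. What stands is that this option is not chosen, the visits it would use are not stated, and step 5 shows it does not cure outcome-dependent loss.

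A reader might also infer that patients who stop for drug-related reasons leave the study. Protocol 11.1 does not say so. It concerns treatment, lists withdrawal of consent as one circumstance among several, and is silent on follow-up. The synopsis speaks of all enrolled subjects completing six months. That is a general definition of study completion, not a retention rule, so the gap is silence rather than exclusion.

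Unequal loss is not established either. Protocol 12.2 reports that hypotension in earlier trials was not linked to more discontinuation, and that no increased risk of angioedema was indicated. Protocol 11.1.1 sets out steps to take before hypotension leads to stopping. These points lower the likelihood of unequal loss without removing it.

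Finally, the baseline-driven bias in step 3 is modest, and the plan already permits the adjusted ANCOVA that removes it. This is fair. It is an argument for making that adjustment mandatory, not for leaving it optional.

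**Conclusion.** The concern holds as a gap in specification. Efficacy is promised on all randomised patients, but nothing in either document fixes the model, requires baseline, states a missing-data assumption, tests that assumption, or says whether patients off drug are assessed at week 26. An unadjusted completer comparison is compatible with the plan as written.

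The size is hypothetical because the documents give neither dropout by arm nor the baseline correlation. With 11–19% loss mainly in one arm, dependent on baseline at correlation 0.5, the unadjusted estimate is off by about 0.08–0.15 (9–17% of 0.898) and the adjusted one is about unbiased. If loss depends on the unseen outcome, bias remains after adjustment: 0.12–0.22 under the assumptions of step 4.

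A reader might conclude that the bias must flatter LCZ696. That is so only if the LCZ696 patients who are lost have higher PCWP/CI. Patients stopping for hypotension need not, and if theirs is lower the bias runs the other way.

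**What to change.** 1. **SAP 1.2.** Name one primary model with baseline PCWP/CI mandatory: baseline-adjusted ANCOVA, or the equivalent constrained-baseline two-visit mixed model, which includes every randomised patient with a baseline test. State that it assumes week-26 values are missing at random given arm and baseline.
2. **Sensitivity analysis and reporting.** Add a tipping-point analysis by delta-adjusted multiple imputation, for example shifting imputed LCZ696 values by 0 to 1 SD (0 to 1.5). Since the direction is unknown, shifts the other way are worth showing too. Report how many patients in each arm have a week-26 value, and the reasons for those who do not.
3. **Protocol 11.1, if follow-up is still open.** State that stopping study drug is separate from withdrawing consent, and that patients who stop are still asked to attend the already planned week-26 assessments unless consent is withdrawn or a test is contraindicated. This concerns data collection only and leaves the treatment rules as they are.

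Item 3 may come too late: the SAP is dated 07022024, and Protocol section 7 planned the last visit for July 2020. The documents do not say when follow-up actually ended. Items 1 and 2 use data already collected and apply either way.

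The cost is a paragraph in the SAP and a little more analysis. Item 3 would be a protocol change that asks patients off drug to have an invasive test, so it would need the usual approvals, and some patients will decline.
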